7.1.5 Sensitivity Analyses

For the primary and key secondary endpoints the following sensitivity analyses will be provided:

- 1) To investigate the MAR assumption 2 sensitivity analyses will be provided:
 - a) analysis with control-based pattern imputation
 - b) analysis with tipping-point approach (SAS example provided in reference Section¹)

The details of the MAR assumption sensitivity analyses are given below. P-values will be provided for these sensitivity analyses.

- 2) Longitudinal Repeated Measures analysis (as described in [Section 7.1.3](#)) removing the interaction terms for the stratification variables by time. P-values will be provided for these sensitivity analyses
- 3) Analyses based on the full ITT population including all randomized subjects and all observations obtained on or off study treatment. The protocol specifies to collect for all randomized subjects the planned efficacy measurements at each time point up to the end of the Week 24 Double-Blind Period also in the case a subject is off treatment. Therefore the expectation is that these measurements also be available for a randomized subject after the subject prematurely discontinues treatment and for a randomized subject who was never treated. The longitudinal repeated analysis model used for the primary analysis will be repeated, but for this sensitivity analysis the full ITT population will be used and all measurements collected on and off treatment up to Day 169 will be included in the analysis. P-values will be provided for these analyses.
- 4) The sensitivity analysis described in 3) including all efficacy measurements collected on and off treatment up to Day 169 will be repeated for all randomized and treated subjects (modified ITT population instead of ITT population described in bullet 3).

The sensitivity analyses described in bullet 1) will only be provided if there are at least 10% of subjects with missing data (for the corresponding efficacy measure) at Day 169 in either treatment group.

The sensitivity analyses including measurements on and off treatments (bullet 3) and 4)) will only be provided if:

- at Day 169 there are at least 10% of subjects with missing data (for the corresponding efficacy measure) in either treatment group for the primary analysis
- and on top, at Day 169 there are at least 10% more non-missing data (for the corresponding efficacy measure) in either treatment group using all collected data (including off treatment measures) compared to number of non-missing efficacy measurements in primary analysis

[REDACTED]

[REDACTED]

[REDACTED]

Each of the 100 imputed datasets will be analyzed using the same MMRM as the primary efficacy analysis. Results from the analyses of each imputed dataset, i.e. least squares (LS) mean treatment differences and their standard errors, will be combined using Rubin's imputation rules (using the SAS MIANALYZE procedure) to produce a pooled LS mean estimate of treatment difference, its 95% CI, and a pooled p-value for the test of null hypothesis of no treatment effect.

The above control-based imputation will also be done for the key secondary endpoints of ESSPRI and Stimulated Whole Salivary Flow.

Tipping Point Analysis

Sensitivity to departures from the MAR assumption will also be investigated using a tipping point analysis. In this analysis, departures from MAR in the abatacept group will be assessed assuming that subjects who discontinue the study have, on average, efficacy outcomes after discontinuation that are worse by some amount δ compared to other similar subjects with observed data (i.e., compared to a value which would have been assumed under a MAR model).

A series of analyses will be performed with increasing values of δ until the analysis conclusion of a statistically significant treatment effect no longer holds. The value of δ that overturns the primary results will represent a tipping point. An interpretation of clinical plausibility of the assumption underlying the tipping point will be provided.

Change from baseline in ESSDAI total score at Week 24 will be analyzed based on data observed while the subject remains on treatment as well as data imputed using multiple imputation methodology for time points at which no value is observed. Intermittent (non-monotone) missing data will be imputed first based on the MAR assumption and a multivariate joint Gaussian imputation model using MCMC method within each treatment arm, as described above for the pattern mixture model with control-based imputation.

The remaining monotone missing data will be imputed using sequential regression multiple imputation, where a separate regression model is estimated for imputation of each variable (i.e., measurement at each time point). Each regression model will include explanatory variables for treatment, stratification variables (current use of oral corticosteroids, current use of hydroxychloroquine, by stimulated salivary flow ($< 0.1\text{mL}/\text{min}$, $\geq 0.1\text{mL}/\text{min}$) and Japan.) and all previous (Baseline, Weeks 4, 8, 12, 16, 20) values of ESSDAI total score.

Imputed data will consist of 100 imputed datasets. The random seed number for partial imputation with the MCMC method and for the sequential regression multiple imputation will be 12345.

After the MAR-based imputations have been generated for ESSDAI total score at each time point, a value of δ will be added to all imputed values in the abatacept group prior to analyzing the imputed data. This approach assumes that the marginal mean of imputed subject measurements is worse by δ at each time point after discontinuation compared to the marginal mean of subjects with observed data at the same time point.

Each of the 100 imputed and δ -adjusted datasets will be analyzed using the same MMRM as the primary efficacy analysis. Results from the analyses of each imputed dataset, i.e. LS mean treatment differences and their standard errors, will be combined using Rubin's imputation rules (using the SAS MIANALYZE procedure) to produce a pooled LS mean estimate of treatment difference, its 95% CI, and a pooled p-value for the test of null hypothesis of no treatment effect.

Analyses will be conducted with different values of δ at each visit, which present a percentage of the LS mean treatment difference at that visit, starting at 5% with 5% increments, until either the tipping point is identified (i.e. where a statistically significant treatment effect no longer holds).

In case there are issues with the multiple imputation analysis including the 4 randomization stratification variables, the first back-up model is to exclude the Japan and stimulated salivary flow randomization stratification factors. The second back-up model is to exclude all randomization stratification factors.

7.1.6 Outliers

The 'influence' option of the SAS procedure PROC MIXED will be included in the longitudinal repeated measures analysis to explore if there are subjects with outlying observations that have an impact on the changes from baseline at Day 169 for the primary and 2 key secondary endpoints. Subjects with a high restricted likelihood distance compared to other subjects will be identified. The impact of these outlying subjects on the result at Day 169 will be investigated by deleting the

subjects and submitting the analysis model without these subjects (sensitivity analysis). A plot of the restricted likelihood distance per subject and per treatment group will be provided.

7.2 Study Conduct

Relevant protocol deviations, which could have an impact on the primary endpoint, will be identified for all subjects who are randomized and receive study medication during the Double-Blind Period. Details of relevant protocol deviations are provided in [APPENDIX 2](#).

All subjects with relevant protocol deviations that could affect the primary efficacy will be identified prior to database lock and unblinding of treatment assignment. All relevant protocol deviations will be listed and summarized by treatment group. The subjects identified with relevant protocol deviation will not be excluded from any analysis population described in [Section 6.3](#). If at least 10% of the subjects in one of the treatment arms in the modified ITT analysis population demonstrate relevant protocol deviations, a per-protocol analysis will be performed for the primary endpoint, change from baseline in ESSDAI at Day 169. The per-protocol analysis will exclude data from subjects with relevant protocol deviations as specified in [APPENDIX 2](#).

7.3 Study Population

7.3.1 Subject Disposition

The disposition of subjects will be summarized for the pre-treatment period, Double-Blind Period, open-label period and follow-up period. The disposition of subjects will also be represented graphically with a flow-chart for the same periods.

The summary of subject disposition for the pre-treatment period will be based on all enrolled subjects. It will include a summary of the:

- number of subjects enrolled
- number (percentage) of subjects randomized
- number of subjects randomized and treated by treatment group
- number of subjects randomized but not treated by treatment group
- number (percentage) of subjects per reason for not being randomized.
- number (percentage) of subjects per reason for being randomized, but not treated.

Percentages will be based on a denominator of all enrolled subjects. The reasons for not being randomized or being randomized but not treated will also be listed

The summary of subject disposition for the Double-Blind Treatment Period (as defined in [Section 6.1](#), is on-treatment period) will be based on the modified ITT analysis population and will summarize by treatment group the:

- number (percentage) of subjects completing the treatment in the Double-Blind Treatment Period

- number (percentage) of subjects not completing the treatment the Double-Blind Treatment Period (i.e. early discontinued treatment subjects)
- number (percentage) of subjects per reason for not completing the treatment in the Double-Blind Treatment Period (i.e. reasons for early discontinuation of treatment)
- number (percentage) of subjects who completed treatment in the Double-Blind Treatment Period and treated in open-label period
- number (percentage) of subjects who completed treatment in the Double-Blind Period and not treated in open-label period
- number (percentage) of subjects per reason for completing the double-blind treatment and not treated in open-label period

Percentages will be based on a denominator of all randomized and treated subjects (modified ITT population). The reasons for not completing treatment in the Double-Blind Treatment Period or for not being treated in open-label will also be listed.

According to the protocol, patients who discontinue treatment in the Double-Blind Period should continue the study off treatment up to Day 169 to be assessed for efficacy. A CRF is collecting if a subject (on or off treatment) is continuing up to Day 169 or not. The summaries detailed below will provide the reasons for discontinuation on or off treatment prior to Day 169. The summary of subject disposition for the Double-Blind Period (on and off treatment up to Day 169) will be based on the modified ITT analysis population and will summarize by treatment group the:

- number (percentage) of subjects completing the Double-Blind Period (on and off treatment combined) up to Day 169
- number (percentage) of subjects who discontinued treatment and did not continue in the study up to Day 169
- number (percentage) of subjects per reason for not continuing in the study up to day 169 (after subject discontinued the treatment)

Percentages will be based on a denominator of all randomized and treated subjects (modified ITT population). The reasons for not completing in the Double-Blind Period (on or off treatment) or for not being treated in open-label will also be listed.

The summary of subject disposition for the open-label treatment period will be based on the Open-Label Population analysis population and will summarize by treatment group the:

- number (percentage) of subjects completing the open-label period
- number (percentage) of subjects ongoing in the open-label period (i.e. entering Open-label period but not completed or discontinued at the time of lock)
- number (percentage) of subjects not completing the open-label period (i.e. early discontinued subjects)
- number (percentage) of subjects per reason for not completing the open-label period (i.e. reasons for early discontinuation)
- number (percentage) of subjects continuing in the study (i.e. entering in the follow-up period)

- number (percentage) of subjects not continuing in the study (i.e. not entering in the follow-up period)
- number (percentage) of subjects per reason for not continuing in the study

Percentages will be based on a denominator of all subjects treated in the open-label period. The reasons for not completing the open-label period or for not continuing in the study will also be listed.

The summary of subject disposition for the follow-up period will be based on all subjects who discontinued in the double-blind or who discontinued in the open-label or who completed the double-blind but not treated in the open-label, or who completed the open-label (those subjects are expected to go into the follow-up period) and will summarize by randomized treatment group the:

- number (percentage) of subjects completing the follow-up period
- number (percentage) of subjects not completing the follow-up period
- number (percentage) of subjects per reason for not completing the follow-up period

Percentages will be based on a denominator of all subjects who discontinued in the double-blind or who discontinued in the open-label or who completed the double-blind but not treated in the open-label, or who completed the open-label (those subjects are expected to go into the follow-up period). The reasons for not completing the follow-up period will also be listed.

The number of subjects enrolled, randomized, and treated will be summarized by country and study site.

7.3.2 Demography and Baseline Characteristics

Demographic and baseline disease characteristics will be summarized by randomized treatment group and overall based on the modified ITT analysis population. For continuous variables, they will be summarized using means, standard deviations, median, Q1, Q3 and ranges (minimum and maximum), based on non-missing observations. The distribution of categorical variables will be summarized by treatment group using frequency and percentage. For categorical variables, percentages will be calculated out of the total number of subjects in the modified ITT population, overall and by treatment group (i.e., each denominator includes the number of subjects with missing/unknown values for the characteristic and missing is included as a category).

Table 7.3.2-1: Demographic and Baseline Characteristics

Characteristic	Summarized as	Categories
Age (years)	Categorical and Continuous	< 65 yrs., ≥ 65 yrs. ≤ 50 yrs., > 50 yrs.
Gender	Categorical	Male Female

Table 7.3.2-1: Demographic and Baseline Characteristics

Characteristic	Summarized as	Categories
Race	Categorical	White Black or African American Asian Other
Ethnicity (to be summarized only for USA subjects)	Categorical	Hispanic/Latino Non Hispanic/Latino
Region	Categorical	North America South America Europe Asia ROW (see APPENDIX 3)
Body Weight (kg)	Continuous and Categorical	< 60kg 60 - 100kg > 100kg
Randomization stratification factors as recorded on IWRS	Categorical	Baseline Hydroxychloroquine use (YES/NO) Baseline oral corticosteroid use (YES/NO) Screening and Baseline Stimulated Salivary Flow (< 0.1mL/min, ≥ 0.1mL/min) Japan (YES/NO) and all possible combinations of these 4 stratification factors
Randomization stratification factors as recorded on CRF	Categorical	Baseline Hydroxychloroquine use (YES/NO) Baseline oral corticosteroid use (YES/NO) Screening and Baseline Stimulated Salivary Flow (< 0.1mL/min, ≥ 0.1mL/min) Japan (YES/NO) and all possible combinations of these 4 stratification factors on CRF
2016 ACR-EULAR Classification Criteria met:	Categorical	Yes/No

 • Labial salivary gland with focal lymphocytic sialadenitis and focus score ≥ 1 • Anti-SSA (Ro)+ • Ocular Staining score ≥ 5 (or van Bijsterveld score ≥ 4) on at least one eye • Schirmer ≤ 5mm/5min on at least one eye • Unstimulated whole saliva flow rate ≤ 0.1ml/min 		
ESSDAI Total Score	Continuous	

Table 7.3.2-1: Demographic and Baseline Characteristics

Characteristic	Summarized as	Categories
ESSDAI Total Score	Categorical	Low < 5 Moderate $5 \leq \text{ESSDAI} \leq 13$ High ≥ 14
ESSDAI Constitutional Domain Score	Continuous	
ESSDAI Lymphadenopathy Domain Score	Continuous	
ESSDAI Glandular Domain Score	Continuous	
ESSDAI Articular Domain Score	Continuous	
ESSDAI Cutaneous Domain Score	Continuous	
ESSDAI Pulmonary Domain Score	Continuous	
ESSDAI Renal Domain Score	Continuous	
ESSDAI Muscular Domain Score	Continuous	
ESSDAI Peripheral Nervous System (PNS) Domain Score	Continuous	
ESSDAI Central Nervous System (CNS) Domain Score	Continuous	
ESSDAI Haematological Domain Score	Continuous	
ESSDAI Biological Domain Score	Continuous	
ESSPRI Total Score	Continuous	
ESSPRI - Pain Score	Continuous	
ESSPRI- Fatigue Score	Continuous	
ESSPRI - Dryness Score	Continuous	
Stimulated whole saliva secretion	Continuous	
DAS28-CRP at Day 1	Continuous	
DAS28-CRP at Day 1 <	Categorical	DAS28-CRP ≤ 2.6 DAS28CRP > 2.6
DAS28-CRP at Day 1 <	Categorical	DAS28-CRP ≤ 3.2 DAS28CRP > 3.2

7.3.3 General Medical History

The number (percent) of subjects with general medical history findings before the first study medication will be summarized by treatment group and overall using the modified ITT analysis population. A corresponding listing of medical history findings will be provided.

7.3.4 Prior Medication and Medication at Day 1

Prior medications are defined as medications with a start date prior to the first day of Double-Blind Treatment Period.

Prior medication of special interest and medication of special interest at Day 1 will be summarized for the 2 treatment arms. The results will be based on the modified ITT analysis population. The medication of special interest are defined in [Section 7.4.4](#).

Missing and partial date handling of start and stop dates of prior medications, is described in [Section 8.4](#). The World Health Organization (WHO) dictionary is used to code non-study medications.

7.4 Extent of Exposure

7.4.1 Study Therapy

The extent of exposure during the double-blind (for the As-treated Analysis Population) and the cumulative abatacept periods (for the cumulative abatacept population) will be summarized in the following ways:

- Number of abatacept/placebo injections
- Number of days a subject is known to be on study drug.

The number of injections subjects received will be based on the study medication page of the CRF when it is indicated that a subject received the study medication.

The number of days the subject is known to be on study drug (exposure to study drug) during the Double-Blind Period is calculated as:

For subjects who discontinued during the Double-Blind Period OR completed the Double-Blind Period but not treated in open-label period OR not treated in the open-label period within 56 days of the last injection in the Double-Blind Period:

Exposure in days = (date of last injection in the Double-Blind Period - date of first injection in the Double-Blind Period + 1) + 56.

For subjects who were treated in the open-label within 56 days of the last injection of the Double-Blind Period:

Exposure in days = (date of first injection in the open-label period - date of first injection in the Double-Blind Period).

Exposure in cumulative abatacept period for subjects who discontinued treatment in double-blind or open-label OR who completed double-blind and not treated in Open-label or who completed open-label is calculated as:

Exposure in days = (date of last abatacept injection - date of first abatacept injection + 1) + 56

In case a patient randomized to abatacept does not go into open-label within 56 days post last dose in double-blind, the exposure has to be adjusted for the gap exceeding 56 days.

Exposure in cumulative abatacept period for subjects who are on-going in open-label period is calculated as:

Exposure in days = cut-off date - date of first abatacept injection with cut-off date = the date database lock date.

For subjects randomized to placebo, the date of first abatacept injection is date of first open-label abatacept treatment. For subjects randomized to abatacept, the date of first abatacept injection is the date of first double-blind abatacept treatment.

The date of last abatacept injection can be the last date of abatacept in double-blind if the subject is not treated in open-label or the date of last abatacept injection in open-label if subject is treated in open-label.

The offset of 56 days is the length of 2 regular dosing cycles and represents approximately 4 times the half-life of abatacept in humans.

Summaries of exposure to study drug during the Double-Blind Period and the cumulative abatacept period will show the distribution of the number of injections and days on drug, together with the means, standard deviations, medians, minimum and maximum. For the Double-Blind Period the presentation will be by treatment group and for the cumulative abatacept period all subjects will be presented together.

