3.3.1 Inclusion Criteria

1. Signed Written Informed Consent

- a. Subject is willing to participate and has signed informed consent.

2. Target Population

- a. Subjects must meet the proposed 2015 ACR/EULAR Classification Criteria for SS (Sjögren’s Syndrome) ([Appendix 3](#)), as specified for pSS (primary Sjögren’s Syndrome).

- i. If a prior labial salivary or parotid gland biopsy was performed, information will be reported in the CRF and the report should be obtained for the source documents.
- b. Subjects should have pSS that is refractory to symptomatic or local therapy (eg, NSAIDs).
- c. ESSDAI \geq 5 at screening.
- d. Positive anti-SSA/Ro at screening.
- e. Stimulated salivary flow of at least 0.1 mL/min at screening and randomization in at least 124 subjects (72%). Enrollment of subjects with less than 0.1 mL/min of stimulated salivary flow at screening and/or randomization may be closed after 48 of such subjects are randomized.
- f. Subject Re-enrollment: This study permits the re-enrollment of a subject that has discontinued the study as a pre-treatment failure (ie, a “screen failure”, the subject has not been randomized / has not been treated). If re-enrolled, the subject must be re-consented and will receive a new PID.

3. Age and Reproductive Status

- a. Males and Females, ages \geq 18 (or age of majority).
- b. Women of childbearing potential (WOCBP) must have a negative serum or urine pregnancy test (minimum sensitivity 25 IU/L or equivalent units of HCG) within 24 hours prior to the start of study drug.
- c. Women must not be breastfeeding.
- d. Women of childbearing potential (WOCBP) must agree to follow instructions for method(s) of contraception for the duration of treatment with study drug(s) (abatacept/placebo) plus 5 half-lives of study drug (70 days) plus 30 days (duration of ovulatory cycle) for a total of 100 days post-treatment completion.
- e. Males who are sexually active with WOCBP must agree to follow instructions for method(s) of contraception for the duration of treatment with study drug(s) (abatacept/placebo) plus 5 half-lives of the study drug (70 days) plus 90 days (duration of sperm turnover) for a total of 160 days post-treatment completion. In addition, male subjects must be willing to refrain from sperm donation during this time.

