7.6.2.8 Multiple Adverse Events

Several descriptive summaries of adverse events that takes into account the number of occurrences that an AE was reported by individual patients will be provided. In order to prepare these summaries, the CRF data will be processed according to standard BMS algorithms to categorize each line of patient data as a new occurrence or a continuation of an existing event. This determination will be based upon onset and resolution dates. Each line of patient data will represent the maximum severity observed as well as the last known assessed relationship to study medication by the investigator.

This data will be presented as the rate per 100 years of patient exposure. Exposure to study medication will be calculated according to approved standard BMS algorithms as well.

As an example, if 5 patients report 7 unique episodes of headache and had a combined cumulative exposure of 20 years to study medication, the incidence rate is reported as $7 / 20 * (100)$ or 35 cases per 100 patient years of exposure.

The following summary tables will be provided:

- A table showing the total number and rate (exposure adjusted) of occurrences for all AEs occurring in at least 5% of the subjects treated will be presented for the double-blind treatment period and the cumulative abatacept period separately.
- For all AEs as well as for AEs of special interest:
 - A table showing total number of events and rate (exposure adjusted) will be presented for the Double-Blind Treatment Period (overall) and the cumulative abatacept period (by 6 months time intervals) separately.
 - A table showing the number of subjects experiencing an AE once or multiple times will be presented for the Double-Blind Treatment Period and the cumulative abatacept period separately.

- Listing displaying the unique instances of all AEs, i.e., after duplicates have been eliminated and overlapping and contiguous occurrences of the same event have been collapses.

No formal comparisons are made between treatments. No formal statistical testing will be performed, only summary statistics are provided.

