9 CONTENT OF REPORTS

The results of this study will be presented in a standard BMS Clinical Study Report (CSR).

CSR Primary analysis Month 6:

At the time of the primary analysis (i.e. after all subjects complete the Double-Blind Period), the final efficacy and safety analysis up to Day 169 will be provided (Double-Blind Period). In addition, all available safety data will be summarized for the cumulative abatacept period up to Year 1 (interim analysis). No efficacy analysis beyond Day 169 will be provided.

CSR Year 1:

This CSR will include the final analysis for Year 1 (efficacy and safety).

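### Cumulative abatacept exposure runs to database lock for on-going subjects, and 56 uncapped days past the last dose for the rest, so some counted days are not documented exposure

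*SAP*

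**What the plan says.** SAP 7.4.1 names the summary measure "Number of days a subject is known to be on study drug". In the cumulative abatacept period it is derived by two rules:

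- **On-going in open label:** "Exposure in days = cut-off date - date of first abatacept injection with cut-off date = the date database lock date". No dose, visit or contact date enters. SAP 7.3.1 describes such subjects as "ongoing in the open-label period (i.e. entering Open-label period but not completed or discontinued at the time of lock".
- **Stopped or completed:** "Exposure in days = (date of last abatacept injection - date of first abatacept injection + 1) + 56". The offset is explained thus: "The offset of 56 days is the length of 2 regular dosing cycles and represents approximately 4 times the half-life of abatacept in humans". No upper limit is set at last contact or at lock.

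The injection count in the same section comes from the CRF, so it stops at recorded doses.

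On the adverse event side, SAP 7.6.2.8 says "This data will be presented as the rate per 100 years of patient exposure", but takes the exposure from the sponsor's standard algorithms and does not refer to 7.4.1. SAP 9 says that at the Month 6 report "all available safety data will be summarized for the cumulative abatacept period up to Year 1 (interim analysis". That is the lock at which on-going subjects occur.

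**The concern.** Open-label injections between visits are documented on diary cards (Protocol 4.7), which are collected at visits 28 days apart (Protocol Table 5.1-3). Dosing after the last collected card is presumed. Protocol 3.5 requires withdrawal in open label only after more than six consecutive missed doses or more than ten in total. Protocol 3.7.2 requires several documented contact attempts before a subject counts as lost. A subject can therefore be off drug or out of touch and still accrue days to lock.

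The 56-day offset raises a related problem. It can be credited to someone whose contact ended at the last dose, and it can run beyond the lock. SAP 2.1 also excludes from the follow-up period subjects who move to post-study abatacept.

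At stake is whether person-time matches the period in which events could be recorded. Person-time with incomplete event recording lowers any rate that uses it as denominator.

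**Working it through.** **1. The plan's own figures.** The worked example in SAP 7.6.2.8 reproduces: 7 episodes / 20 years × 100 = 35 per 100 patient-years. The offset is also coherent. Protocol 3.3.1 has "plus 5 half-lives of study drug (70 days", so one half-life is 70/5 = 14 days, and 4 × 14 = 56 days.

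**2. Gap between last contact and lock (assumption).** The documents state none. With 28-day visits (±3 days) and data entry current at lock, the gap averages about 14 days and reaches about 28 to 31. A longer gap needs data entry to stop before lock.

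**3. Overrun in an on-going subject.** With observed exposure E and gap g, the share of stated exposure that is undocumented is g/(E + g). E of 200 to 300 days is assumed.

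| g (days) | E = 300 | E = 200 |
|---|---|---|
| 14 | 14/314 = 4.5% | 14/214 = 6.5% |
| 28 | 28/328 = 8.5% | 28/228 = 12.3% |
| 56 | 56/356 = 15.7% | 56/256 = 21.9% |

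The last row applies only if entry closes about a month before lock.

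**4. Pooled table.** The report combines on-going subjects with the rest. Assume that all 172 subjects continue, recruitment is uniform over 180 to 540 days, and lock falls 0 to 60 days after the last Day 169.

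- With gaps of 14 to 31 days, the on-going overrun is between 1.7 of 141 patient-years (1.2%) and 14.0 of 82 (17.0%).
- If entry closes 30 to 60 days before lock (gap 58 to 88 days), it is 6.1% to 27.2%.
- If this exposure were the denominator and no event were recorded in the overrun, a rate of 35 would be reported as 35 × (1 − 0.012) = 34.6 down to 35 × (1 − 0.170) = 29.0.

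**5. Lock rule against the 56-day rule.** Lock − first exceeds (last − first + 1) + 56 only when lock − last is more than 57 days. At a gap of 14 days the lock rule gives 57 − 14 = 43 days fewer; at 28 days, 57 − 28 = 29 fewer.

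**6. Offset past lock.** A subject whose last injection was d days before lock (d below 56) is credited with 56 − d days after lock: 46 days for d = 10, 28 days for d = 28. No event in those days can be in the locked database.

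**7. The missing day.** The on-going formula omits the + 1 in the rule for stopped or completed subjects. This shortens exposure by one day, against the direction of the overrun.

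**The case against.** The case against is substantial.

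- **Rates.** A reader might infer that the Month 6 event rates are diluted and the drug made to look safer. The documents do not establish this: 7.6.2.8 takes its denominator from sponsor algorithms that are not reproduced. The cumulative summary is also one combined group with no comparator. This stands.
- **Overstatement.** A reader might infer that on-going subjects are over-credited by the SAP's own standard. Step 5 shows that, with current data entry, they get fewer days than the last-dose-plus-56 convention would give. This stands. What remains is that days after the last collected diary card are not known days.
- **Empty time.** It would be too strong to say that no event can arise between last visit and lock. Protocol 6.1.1 requires serious events to be reported within 24 hours of awareness, independent of visits. The lag mainly threatens non-serious events. Only days after lock are empty by construction.
- **Size.** Figures near 20% need a gap of about 56 days. Under monthly visits with current entry, 28 days is close to the maximum, not the minimum.
- **The offset is a risk window.** Adverse events are counted over the same 56 days (SAP 6.1 and 7.6.1), and follow-up visits support it. This is fair for subjects who are followed. It does not cover those whose contact ended sooner, or days after lock.
- **Consistency.** Cutting only on-going subjects at last contact would credit people on drug with less time than people off it. This is correct, so any cap has to apply to everyone.

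**Conclusion.** The point holds as a minor one. Two stated rules count person-time that is not tied to data collection, under a label that says the days are known. For on-going subjects the overrun is about 4 to 7% at an assumed 14-day gap and 9 to 12% at 28 days, both with 200 to 300 days of observed exposure. It is larger only if data entry closes well before lock. The pooled share depends further on assumed recruitment and lock timing.

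The reach is narrow. Double-blind exposure does not use the lock date, adverse event proportions use subject counts, and on-going subjects should not occur in the final Year 1 analysis. Any effect on exposure-adjusted rates depends on an algorithm that the documents do not show.

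**What to change.** In SAP 7.4.1, define a data cut-off date and apply it to both adverse events and exposure. For every subject in the cumulative abatacept period, end exposure at the earliest of last abatacept dose + 56 days, last recorded contact and the data cut-off, with the same + 1 convention throughout. Define last recorded contact so that an adverse event report counts as contact; otherwise an event could fall outside its own person-time. In 7.6.2.8, state that this person-time is the denominator of the rates per 100 patient-years.

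The cost is SAP wording and derivation code, with no new data collection. Reported exposure becomes slightly shorter.
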